## 9 Procedures: FCX-007 Administration to Wound(s)

#### 9.1 Selection

A preliminary evaluation of target wounds will occur at the Screening Visit. Potential wounds that meet criteria will be identified at Screening and followed throughout the Wound Monitoring Period. New wounds may also be identified during the Wound Monitoring Period. Final target wound and wound pair selection will occur on Visit 2 based on meeting the following criteria:

- 1. The total injection area (circumference plus the lengths of the axes) is a maximum of approximately 54 linear cm (see **Figure 4** for more details).
- 2. If more than one pair of wounds is identified, the sum of the injection areas a maximum of approximately 54 linear cm.
- 3. If multiple pairs of wounds are identified that meet criteria, wounds with the most consistent wound areas throughout the Wound Monitoring Period are to be selected for the study.

If no wound meets criteria 1 and 2 above, a smaller region of a larger wound may be selected for treatment if it can be matched to a similar area of a larger wound as the control. When selecting a smaller region appropriate for treatment, every effort should be made to minimize the border between the treated and the untreated regions of the wound (See **Figure 6B**). Ideally, a narrow peninsula off the main portion of the wound should be selected for administration of FCX-007.

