#### 9.1.2 Pairing and Labeling of Selected Wound Pairs

Potential target wounds will be identified by a continuous sequential numbering of Pair 01 (P01) through Pnn. Depending on the size of the largest wound in the pair, the investigator may select up to three pairs of wounds for inclusion in the study. Because the Investigator will not know which of the two paired wounds will be randomly assigned to receive FCX-007, it should be assumed that the largest of the two wounds will receive FCX-007 when calculations are made to determine

CONFIDENTIAL Page 41 of 75

[figure not shown]
Phase I/II Protocol Final Version 8.0, 29 Oct 2019

how many wound pairs to select. The final selected target wound pairs will be labeled as T1A and T1B for the 1st pair, T2A and T2B for the 2nd pair, and T3A and T3B for the 3rd pair.

The pairs should be ordered from smallest to largest; T1A and T1B will have the smallest injection area, T2A and T2B will have the next smallest injection area, etc. On the day of administration, the smallest wounds will be injected first, the second smallest second, etc.

**Figure 4** provides an example and sample calculations for a subject in which two pairs of wounds are selected for inclusion in the study. As shown in the example below, if more than one pair of wounds is identified, the sum of the injectable areas of the largest wounds in the pair must be less than or equal to 54 linear cm. Wounds should be selected with the intent to administer investigational product to the entire injectable area of the target wounds.

Figure 4 - Wound Pairing and Selection Calculations Example

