## 9.2 Treatment Assignment of Paired Wounds

Paired wounds will be randomly assigned to receive FCX-007 or no treatment.

On Visit 2, during the selection of the target wounds, each wound of up to three target wound pairs will be labeled by the investigator as T1A and T1B for the 1st pair, T2A and T2B for the 2nd pair, and T3A and T3B for the 3rd pair. Following the determination of target wound pairs, the Investigator will assign each wound to either active treatment or no treatment randomly.

CONFIDENTIAL Page 42 of 75

Fibrocell Technologies RDEB Phase I/II Protocol Final Version 8.0, 29 Oct 2019

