#### 9.4.2.1 Treatment of Partial Wounds

[figure not shown]
It is preferable to inject whole wounds and not partial wounds; however, partial wounds should be used if whole wounds that meet criteria are not available.

Figure 6 – Example Target Wound, Injection Sites and Biopsy Locations

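### For partial wounds, Section 9.1 designates the region for FCX-007 by shape and then matches a control to it, which contradicts the rule in 7.3.2, 9.1.2 and 9.2 that pairs are chosen first and then randomised.

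*Combined protocol and SAP*

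**What the plan says.** **Partial wounds.** Section 9.1 applies when no wound meets the first two size criteria. Then "a smaller region of a larger wound may be selected for treatment if it can be matched to a similar area of a larger wound", the latter serving as control. While choosing the region for treatment, "every effort should be made to minimize the border between the treated and the untreated regions of the wound". The preferred shape follows: "Ideally, a narrow peninsula off the main portion of the wound should be selected for administration of FCX-007". Section 9.4.2.1 prefers whole wounds but says that "partial wounds should be used if whole wounds that meet criteria are not available".

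**Allocation.** Section 9.2 states: "Paired wounds will be randomly assigned to receive FCX-007 or no treatment". On order and responsibility it adds: "Following the determination of target wound pairs, the Investigator will assign each wound to either active treatment or no treatment randomly". Section 9.1.2 bases its size calculation on the allocation being unknown at selection: "Because the Investigator will not know which of the two paired wounds will be randomly assigned to receive FCX-007", the larger wound is assumed to be the treated one. Section 7.3.2 lists random assignment within each pair as a Visit 3 procedure. None of these places exempts partial wounds.

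**Analysis.** Section 14.6.3 names partial wounds alongside whole wounds in the treated-versus-control comparisons. It plans no separate summary of partial-wound pairs.

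**The concern.** The within-subject comparison of treated and untreated wounds is the efficacy objective (Section 2.2.2). Random assignment within the pair makes the two members exchangeable when the drug has no effect. For partial wounds, 9.1 runs the other way round: the region to be injected is chosen first and by shape, and the control need only be similar. The border and peninsula instructions are attached to the region meant for treatment.

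A site cannot reliably obey both sets of instructions. If it randomises a peninsula against a region of another shape, the peninsula will be the untreated control half the time, contrary to 9.1. If it follows 9.1, the treated member is settled before 9.2 is reached. Both can be satisfied only when both regions are peninsulas, which 9.1 does not ask for.

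If the treated region is fixed by shape, and shape influences closure, the comparison for those pairs is open to selection bias that later analysis cannot remove.

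**Working it through.** The plan has no figure to reproduce. Section 14.1 says that no formal sample size calculation was done, and no effect size or share of partial wounds is given. The calculations below are therefore illustrations on stated assumptions.

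**1. Order of steps**

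| Step | 9.1, partial wounds | 7.3.2, 9.1.2 and 9.2, all pairs |
|---|---|---|
| First | Choose the region for FCX-007, ideally a peninsula | Choose both members, allocation unknown |
| Second | Find a region to be "matched to a similar area of a larger wound as the control" | Label the members A and B |
| Third | Nothing left to assign | Assign at random |

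**2. Does shape matter?** Assume that closure comes only from intact skin edges, at an equal ingrowth *d*, with none across the open border. Both regions are 2 x 5 cm (10 cm²).

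- Peninsula, open at one 2 cm end: skin edge 5 + 5 + 2 = 12 cm. Area still open = (2 − 2d)(5 − d).
- Control with one 5 cm skin edge: healed area = 5d.

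| d (cm) | Peninsula open (cm²) | Peninsula healed | Control healed |
|---|---|---|---|
| 0.25 | 1.5 × 4.75 = 7.125 | 28.75% | 1.25/10 = 12.5% |
| 0.5 | 1 × 4.5 = 4.5 | 55% | 2.5/10 = 25% |
| 1.0 | 0 | 100% | 5/10 = 50% |

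At 0.5 cm the two regions fall in adjacent categories of the Section 9.3.1 scale (50-74% and 25-49%) with no drug effect. For 3 x 6 cm regions at 0.5 cm, the peninsula heals 1 − (2 × 5.5)/18 = 39%. A control with one long skin edge heals 0.5/3 = 17%, and one with one short skin edge 0.5/6 = 8%. If the control is a peninsula of the same size, the difference is 0 in every case.

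**3. What could this do to a test?** Section 14.2 plans exploratory two-sided tests at 0.05. Take an exact sign test on independent pairs, with 12 pairs (one per subject in 12 subjects) or 36 (12 × 3, the maximum for 12 subjects). Let q be the assumed chance, with no drug effect, that the treated member of a partial, non-randomised pair looks better. Let f be the assumed share of such pairs. The chance averaged over all pairs is fq + (1 − f) × 0.5. For example, f = 0.25 and q = 0.8 give 0.575.

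| Pairs (reject at) | f | q = 0.6 | q = 0.7 | q = 0.8 |
|---|---|---|---|---|
| 12 (≥10 or ≤2) | 0.25 | 0.041 | 0.050 | 0.065 |
| 12 | 1 | 0.086 | 0.253 | 0.558 |
| 36 (≥25 or ≤11) | 0.25 | 0.036 | 0.059 | 0.100 |
| 36 | 1 | 0.162 | 0.609 | 0.958 |

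**4. If both regions are defined first and then randomised**, q = 0.5 whatever their shapes. The actual size of the test is then 0.039 with 12 pairs and 0.029 with 36.

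**The case against.** The strongest reply is that the plan does require randomisation. Sections 7.3.2, 9.1.2 and 9.2 say so for every pair. Section 9.1 concerns selection and 9.2 assignment, so the treatment wording in 9.1 may mean only that a region is suitable for injection. Section 9.1.2 uses similar language about selecting wounds with the intent to inject them, for pairs that it says are randomised. The peninsula sentence is also softened to an ideal. This has weight: a reader might infer from 9.1 that partial wounds are allocated non-randomly by design, and the documents do not support that. What remains is a contradiction, since the peninsula sentence names the region to receive FCX-007 and no section says how to combine that with 9.2.

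A reader might also infer that the peninsula is chosen because it heals faster, or that every partial-wound pair would favour FCX-007. Neither is supported. The only reason given for the shape is a short border between treated and untreated regions. The geometry needs edge-only closure and a control with less skin edge. Requiring a similar control area does not rule out a similar shape, and Figure 6B, which illustrates the partial wound, is not available to check.

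Nor can it be said that a few such pairs would carry the result. Partial wounds are a fallback and their share is unstated. At a quarter of 12 pairs, the illustrated error stays between 0.041 and 0.065. The large values arise only if all pairs are partial and none is randomised.

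**Conclusion.** Wrong as written, as an internal contradiction: for partial wounds, 9.1 cannot be reliably followed together with 7.3.2, 9.1.2 and 9.2. A site that follows 9.1 sets the treated member before randomisation. It does so on a feature tied to skin-bordered perimeter, because for a given region a shorter open border leaves a larger share of the perimeter bordered by skin. Nothing in 14.6.3 would show the consequence.

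Whether a bias arises, and how large it is, cannot be determined from the documents. It depends on edge-driven healing, on a control with less skin edge, and on how many pairs are partial. The 55% versus 25% figure is an assumed worst case; a same-shaped control gives zero. Independence of pairs within a subject was also assumed in the test illustration. Severity is lower than for a confirmatory endpoint: the primary objective is safety (2.2.1) and the statistical tests are exploratory (14.2).

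**What to change.** Reword the partial-wound paragraph of 9.1 along these lines:

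- Define two candidate regions before any assignment.
- Apply the instruction to minimise the border to both regions.
- Match them as far as practicable on area, shape and skin-bordered perimeter, using the imaging software already described in 9.3.
- Label them TnA and TnB, and only then assign one at random to FCX-007 under 9.2.
- Remove wording that names one region for FCX-007 before assignment.

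Randomising after both regions are defined is the essential step. Matching on shape mainly improves precision. Pairs with dissimilar shapes need not be excluded: once randomised they give a valid comparison, exclusion would discard data in a very small trial, and it would conflict with 14.6.3. Keep all partial-wound pairs in the planned comparison and add to 14.6.3 a summary that shows them separately.

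The cost is a short change of wording in 9.1, one extra summary, and slightly more work at wound selection. Some control regions may be harder to find.

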#### 9.1.1 Location and Condition of Wounds

Wounds located on a mucous membrane or covering facial areas are not permitted and wounds with active infection are not permitted. There are no restrictions regarding proximity of paired wounds.

Wounds should appear clean with adequate granulation tissue, excellent vascularization, and not appear infected. Wounds with evidence of active infection are not eligible. Wounds may be debrided, at the discretion of the Investigator, if there is significant crusting or fibrinous debris.

Bacterial cultures will be obtained from potential target wounds on Visit 2 and as needed based upon standard of care and medical judgment of the Investigator.

#### 9.1.2 Pairing and Labeling of Selected Wound Pairs

Potential target wounds will be identified by a continuous sequential numbering of Pair 01 (P01) through Pnn. Depending on the size of the largest wound in the pair, the investigator may select up to three pairs of wounds for inclusion in the study. Because the Investigator will not know which of the two paired wounds will be randomly assigned to receive FCX-007, it should be assumed that the largest of the two wounds will receive FCX-007 when calculations are made to determine

CONFIDENTIAL Page 41 of 75

[figure not shown]
Phase I/II Protocol Final Version 8.0, 29 Oct 2019

how many wound pairs to select. The final selected target wound pairs will be labeled as T1A and T1B for the 1st pair, T2A and T2B for the 2nd pair, and T3A and T3B for the 3rd pair.

The pairs should be ordered from smallest to largest; T1A and T1B will have the smallest injection area, T2A and T2B will have the next smallest injection area, etc. On the day of administration, the smallest wounds will be injected first, the second smallest second, etc.

**Figure 4** provides an example and sample calculations for a subject in which two pairs of wounds are selected for inclusion in the study. As shown in the example below, if more than one pair of wounds is identified, the sum of the injectable areas of the largest wounds in the pair must be less than or equal to 54 linear cm. Wounds should be selected with the intent to administer investigational product to the entire injectable area of the target wounds.

Figure 4 - Wound Pairing and Selection Calculations Example

## 9.2 Treatment Assignment of Paired Wounds

Paired wounds will be randomly assigned to receive FCX-007 or no treatment.

On Visit 2, during the selection of the target wounds, each wound of up to three target wound pairs will be labeled by the investigator as T1A and T1B for the 1st pair, T2A and T2B for the 2nd pair, and T3A and T3B for the 3rd pair. Following the determination of target wound pairs, the Investigator will assign each wound to either active treatment or no treatment randomly.

CONFIDENTIAL Page 42 of 75

Fibrocell Technologies RDEB Phase I/II Protocol Final Version 8.0, 29 Oct 2019

## 9.3 Imaging / Wound Measurement

Target and control wounds will be measured at each indicated visit using the images captured by a Canfield VECTRA H1XP (the "Canfield"). This Canfield handheld imaging system allows for 3D imaging of skin surfaces. The Canfield software offers a comprehensive set of viewing and measurement tools which allow stitching of multiple images into a 3D image as well as allowing calculation of wound perimeter, linear distances and surface area. Investigators will use a restricted set of tools from the software to define both the perimeter and the wound axes for measurement. The software will provide calculations for investigator evaluation of wounds to select for inclusion in the study.

Prior to the first administration of IP, small tattoos will be placed on non-blistered skin near target wounds for the purpose of calibrating the images.

#### 9.3.1 Investigator Assessment of Wound Healing

The investigator will assess wound healing of target wounds (treated and control/untreated) based on the digital images of the target wounds. The investigator will assess wound healing of target wounds from 0% to 100% healed on a categorical scale. The wound healing assessment will be captured in the following categories.

- 0%
- 1-9%
- 10-24%
- 25-49%
- 50-74%
- 75-89%
- 90-99%
- 100%

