### 2.2.2 Secondary

- 1) To evaluate mechanism of action of FCX-007 at visits 5 (Week 4), 6 (Week 12), 8 (Week 25), 10 (Week 52), and unscheduled visits through the evaluation of skin biopsies for C7 expression and the presence of anchoring fibrils.
- 2) To evaluate the efficacy of FCX-007 through an intra-subject paired analysis of target wound area at visits 5 (Week 4), 6 (Week 12), 8 (Week 25), 10 (Week 52), and unscheduled visits, comparing FCX-007 treated wounds to untreated wounds through investigator assessment of wound healing based on the digital images of wounds.

[figure not shown]
CONFIDENTIAL Page 16 of 75

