Proceeding to administration of FCX-007 after a stagger requires that the previous subject complete Week 4 evaluations and the Investigator must have received approval from the Data Safety Monitoring Board (DSMB) to continue the study prior to the next subject's FCX-007 administration.

At a minimum, FDA and DSMB approvals are required for enrollment of pediatric subjects. Local oversight committees may also require approval.

Each phase of the study is divided into four (4) periods: Screening, Wound Monitoring, Treatment, and Long-Term Follow-Up. The Screening Period consists of entry criteria evaluations, the collection of one set of three 3-4 mm biopsies for FCX-007 manufacturing, and the identification and photography of potential target wounds. FCX-007 manufacturing requires about 4 months. This period is the Wound Monitoring Period. Subject target wounds may be imaged a minimum of two times (at least 4 weeks apart) during this period. The purpose of the imaging is to identify wounds with the most consistent wound areas that meet criteria, and to establish a baseline area that takes into account natural wound area variation. The Wound Monitoring Period is expected to have a duration of approximately four months; however, this period can extend beyond four months to accommodate patient scheduling, variations in manufacturing duration and protocol mandated delays (i.e. pauses due to staggered treatment).

After FCX-007 manufacturing is complete, Fibrocell (the Sponsor) and the Investigator will mutually agree on the date of receipt of FCX-007. The duration of the Treatment Period may fluctuate between two and four days. The Treatment Period visits (Day -2 to Day 2) will be scheduled so that the day of dosing (Day 0) is the day of receipt of FCX-007. Prior to dosing, wounds are identified that meet treatment criteria based on imaging results obtained. Up to three pairs of target wounds may be identified for each subject and the Investigator will pair the target wounds according to similarity in wound area.

One wound in each pair will receive FCX-007 and the other wound no treatment.

Safety and proof of mechanism evaluations are conducted during site visits at Visits 5, 6, 8 and 10 (weeks 4, 12, 25, 52), and unscheduled visits. Proof of mechanism will be monitored through assays conducted on biopsies taken from target wounds and areas of intact skin in which FCX-007 was administered.

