#### 9.4.2 Administration

Reference Appendix A: Investigational Product Administration Instructions for detailed instructions regarding the administration of investigational product.

Investigational product is administered intradermally at 1 cm intervals around the periphery of target wounds. The intradermal administration must occur up to 1.0 cm of the wound margin and be administered into the mid-to-superficial dermis. Investigators are to administer 0.25 mL per injection. **Figure 6** provides a graphical depiction of an example target wound showing injection sites and biopsy locations. Locations are shown for (A) treatment of an entire wound, and (B) treatment of a region of a large wound.

[figure not shown]
CONFIDENTIAL Page 44 of 75

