# Appendix A: Investigational Product Administration Instructions

- 1. Intradermal injections are to be administered by the Investigator or an appropriately trained delegated health care professional.
- 2. Administer anesthesia. Subjects will be administered anesthesia per standard of care at the Investigative Site. To minimize pain and discomfort during the investigational product administration, the Investigator should determine the most appropriate anesthetic for each subject, including the use of topical anesthetic cream, local anesthesia, conscious (moderate) sedation, general anesthesia (if undergoing another procedure at time of injection) or a combination thereof. In addition, medication should be considered during and after the injections to treat pain and/or anxiety (i.e. lorazepam).
- 3. Mark the skin as indicated in Section 8.2 (intact skin) and Section 9.4.1 (wounds).
- 4. Approximately 15 minutes prior to the administration of FCX-007, remove the subject's treatment vials from the shipper.
- 5. Resuspend the cells by gently inverting the injection vial three times.
- 6. Tap the top of each vial to release any fluid in the cap prior to opening the vials. Do not dilute the product.
- 7. Unscrew the cap and, using a detachable bore (21-gauge needle), aseptically draw 1.0 mL from one vial.
- 8. Once the product is in the syringe, remove the 21-gauge needle and replace it with the 30-gauge needle for injection of the product. Do not use a 21-gauge needle for injection of the product. Follow sterile technique during this process. Note: Living cells are fragile and should be handled gently, especially when being aspirated into a syringe. Go slowly and use care during this process.
- 9. Hold the syringe using the proper technique: the bevel facing upwards and the arms of the syringe are vertical. Some clinicians may prefer to bend the needle upwards at about a 15-degree angle to facilitate staying in a superficial plane but use of this technique is optional. Grip the syringe with the middle and index finger below the arms, placing the thumb on the upper arm. Do not place the thumb on the plunger while directing the needle into the skin to avoid premature discharge of the product.
- 10. Insert the 30-gauge needle at the first mark.

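### Healing is rated from stored images by the investigator role that assigns the wounds, with no coding or masking; coded reading would cut this bias in part, at modest effort

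*Combined protocol and SAP*

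**What the plan says.** The second secondary objective (section 2.2.2) evaluates efficacy by "comparing FCX-007 treated wounds to untreated wounds through investigator assessment of wound healing based on the digital images of wounds". Section 9.3.1, repeated in 14.6.3.1, gives the method: "The investigator will assess wound healing of target wounds", for treated and control wounds alike, from their digital images. The scale has eight categories from 0% to 100%.

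On who knows the allocation:

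- Section 9.2: "the Investigator will assign each wound to either active treatment or no treatment randomly".
- Section 3.1: "One wound in each pair will receive FCX-007 and the other wound no treatment". There is no sham or vehicle.
- Section 9.4.2: "Investigators are to administer 0.25 mL per injection". Appendix A is wider: "Intradermal injections are to be administered by the Investigator or an appropriately trained delegated health care professional".

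The only place where the plan relies on the investigator not knowing the allocation is pair selection (section 9.1.2), which comes before assignment. A qualified reader is named for the biopsy endpoints (sections 10.2.1 and 10.2.2) but not for healing.

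**The concern.** Percent healed is a judgement. The role that makes it also allocates the wounds, and nothing in the plan keeps the two tasks apart. The control wound is untreated, so nothing at the wound disguises its assignment. Randomising within a pair balances the wounds but does not protect the judgement made about them afterwards.

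Three uses of the rating are exposed:

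- the treated-versus-control comparison in the secondary objective;
- the proportion of wounds closed at 90% or more (section 14.6.3), a cut-off that falls exactly between two adjacent rating categories;
- the third evidence-of-benefit criterion (section 11.1.2.1), which one treated wound can meet and which the DSMB considers before recommending paediatric enrolment (section 11.1.2). Enrolling investigators sit on that DSMB (section 11.1).

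**Working it through.** The plan states no sample size, power or expected closure rate (section 14.1), so there is no figure to reproduce. Three checks were made.

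**1. Does another part of the plan close the gap?** Measured wound area is also analysed (section 14.6.3), but investigators define the perimeter in the software (section 9.3), and 14.6.3 has the investigator assess percent change in area as well. That protection is partial. The biopsy endpoints have a qualified reader, who is not described as masked, and they do not measure healing.

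**2. How far could closure move with no true effect?** Let *p* be the share of treated wounds in the 75-89% category, and *u* the share of those rated one category too high because treatment is known. Both are assumptions; the documents give neither.

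False gain in closure = *p* × *u*

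- Low: 0.10 × 0.25 = 0.025, or 2.5 points
- Middle: 0.20 × 0.25 = 0.05 to 0.20 × 0.50 = 0.10, or 5 to 10 points
- High: 0.30 × 0.50 = 0.15, or 15 points

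Section 14.6.3 compares treatments within each phase. Six subjects with 1 to 3 pairs give 6 to 18 treated wounds. The range is then 0.025 × 6 = 0.15 to 0.15 × 6 = 0.9 of a wound at the small end, and 0.025 × 18 = 0.45 to 0.15 × 18 = 2.7 wounds at the large end.

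**3. What could this do to a test?** The plan sets two-sided tests at 0.05 (section 14.2) but names none for this comparison. As an illustration, assume an exact sign test on independent pairs in which the two wounds always get different ratings. Let *q* be the chance that the rater favours the treated wound when there is no true effect. The chance of a significant result favouring FCX-007 is:

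| Pairs | Needed to favour FCX-007 | q = 0.5 | q = 0.6 | q = 0.7 | q = 0.8 |
|---|---|---|---|---|---|
| 6 | 6 | 0.016 | 0.047 | 0.118 | 0.262 |
| 12 | 10 | 0.019 | 0.083 | 0.253 | 0.558 |
| 18 | 14 | 0.015 | 0.094 | 0.333 | 0.716 |

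The column *q* = 0.5 is what fully effective masking would give. In the other columns the error grows with the number of pairs, so adding wounds does not dilute a rater's tilt. Tied pairs would lower the effective number, and pairs from one subject are not truly independent.

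**Rating load under coded reading.** Subjects × 2 wounds × pairs × visits: 12 × 2 × 1 × 4 = 96 to 12 × 2 × 3 × 4 = 288 over Weeks 4, 12, 25 and 52. If Weeks 16 and 32 are also in the office, it is 12 × 2 × 1 × 6 = 144 to 12 × 2 × 3 × 6 = 432. Reference images and unscheduled visits are extra.

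**The case against.** The strongest reply is that coding will not mask the people available. The investigator finds the wounds at screening, follows them for about four months, then pairs, labels and assigns them. With 1 to 3 pairs per subject, few subjects and at most three sites, a wound may be recognised by body site or shape. Tattoos, biopsies taken close to injection sites (section 10.1.1) and the position of a treated partial wound add cues. A Day 0 image taken after surgical marking could show the injection sites. All of this stands. It means masking would be partial, and that the rater should be someone other than the assigner or injector where possible. It does not justify leaving the labels in view.

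A second reply is timing: ratings are scheduled at each visit, and the DSMB needs Week 4 data. A separate code for each image and locking by visit batch meet most of this. A limit remains, because the first subject in an arm yields only 2 to 6 Week 4 images and shuffling so few hides little. At the transition review, three subjects in an arm yield 6 to 18.

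A third reply is that the inputs to the size are assumed, safety is primary and the tests are exploratory. That is correct and limits the severity.

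A reader might also infer three stronger claims, which the documents do not support:

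- *That the rater is always the person who injected.* Appendix A allows a delegate; the firm ground is assignment of the wounds.
- *That masking the same investigator would work at almost no cost.* The documents say nothing about cost, and recognition is likely.
- *That nothing else informs the comparison.* Measured area gives partial protection, and the biopsy endpoints are read separately.

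**Conclusion.** The point holds as a proportionate improvement. The secondary efficacy comparison rests on a subjective image rating by a role that knows the allocation, and no section provides for coded or masked rating. The illustrative false gain in closure is 2.5 to 15 points, or from a fraction of one wound to nearly three per phase. It rests wholly on assumed values for the share of borderline wounds and the share over-rated. Nothing in the documents shows that such bias has occurred or that a conclusion would change. Severity is limited: safety is the primary objective (section 2.2.1), the analyses are exploratory (section 14.2), and the rating is only one of three alternative benefit criteria, in a paediatric decision that also weighs safety data and needs FDA approval.

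**What to change.** In sections 9.3.1 and 14.6.3.1, state that the healing ratings used to compare treated with control wounds follow these rules:

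- They are made from coded images without treatment or visit label, in random order.
- The rater is an existing investigator or sub-investigator who neither assigned nor injected that subject's wounds, wherever one is available. Record when none was.
- The reference is an unmarked pre-injection image of the same wound, from Visit 2 or from Day 0 before surgical marking.
- Biopsy and injection marks are cropped or covered where possible.
- Each image has its own code, and ratings are locked by visit batch. Week 4 ratings then reach the DSMB without revealing the codes of later images. Images from unscheduled visits join the next batch.

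The cost is modest image handling, some delay between visit and rating, and masking that remains partial. Wound imaging is already scheduled at every on-site visit (Table 2), so no new subject procedure is needed. An added reader is not required either, although one outside the site would mask better. No section makes the Week 4 administration depend on the healing category, so batch rating need not hold it up.
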